MATCHING. Cases and controls will be individually matched to enhance study efficiency and precision with more stable odds ratio estimates and narrower confidence intervals. Matching will be based upon factors which are biologically strong confounders as follows: 1) age (\pm 5 years), 2) gender, 3) race (*white* versus *non-white*) and 4) obesity (BMI $+\text{-}2$ kg/m^2). Recruitment of controls and cases will be contemporaneous given concurrent assessments of eligibility (AF status and matching criteria). To ensure appropriate individual matching on the factors listed above, a staggered recruitment of controls will occur such that matching parameters will change monthly depending upon the distribution of these factors in the case group. Statistical code will be written to perform matching of cases and controls with these five

Elucidation of the Influence of Sleep Apnea on Risk of Atrial Fibrillation PI- [name] and [name]

variables. If exact control matches are not identified, then unmatched cases will be retained in the cue until the next round of matching.

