10. DATA ANALYSIS

EXPOSURES: *Primary:* 1) SDB defined by AHI, i.e. number of apneas + hypopneas/hour of sleep. *Secondary:* 1) Hypoxia: % sleep time with $\text{SaO}_2 < 90\%$, 2) Obstructive Sleep Apnea [obstructive apneas and hypopneas/hour of sleep, obstructive apnea hypopnea index (OAHI)], 3) Central Sleep Apnea [central apneas/hour of sleep, Central Apnea Index (CAI)], 4) Periodic Breathing and 5) EEG arousals [per hour of sleep, Arousal Index (AI)].

OUTCOME: 1) PAF (SA1) and 2) AF burden defined as frequency of AF paroxysms overall and based on self-reported sleep vs. wake (SA2 and 3)

COVARIATES: Age, race, body mass index (BMI, kg/m^2), waist circumference (cm), anti-arrhythmic/beta blocker/calcium channel blocker/ACE inhibitor/angiotensin receptor blocker medications, pacemaker, defibrillator, heart failure (NYHA class), BP, diabetes mellitus, left atrial volume, LVEF, caffeine use, alcohol use and smoking (current versus never smoker or pack years) and activity level. When assessing hypoxia as the relevant exposure, pulmonary disorders will be included as potential confounders.

Table 2. Mediator (SA1) or Outcome (SA3)

Domain	Primary	Secondary	Rationale
Echocardiographic Measures	Left Atrial Volume (ml/m^2)	LA Pressure, LA Systolic Strain, RA area, RA Pressure, LAA Peak Anterograde Flow Velocity (cm/s), Right Atrial Pressure (mmHg), LVEF, LVMI, LVH (concentric LVMI >0.41 , eccentric ≤ 0.41).	Left Atrial Volume predicts risk of AF and PAF ¹⁰³⁻¹⁰⁶ . Secondary measures also associated with AF.
Autonomic Function (Heart Rate Variability)	SDNN (ms) (Time Domain HRV Measure)	Time Domain (r-MSSD (ms), pNN50), Frequency Domain [LF (Hz), HF (Hz), LF/HF], Graphical Parameters (HR patterns, power spectral analysis, Poincaré plots and beat-by-beat HR tachograms) and Novel non-linear measures (e.g. Conditional Entropy ¹⁰⁷).	Reduced SDNN and LF/HF have been identified as AF triggers ⁴⁰ .
Systemic Inflammation	hs-CRP (mg/L)	IL-6 (pg/ml), sIL-6R (ng/mL)	hs-CRP and IL-6 associated with SDB and AF ⁴⁷⁻⁴⁹ . s-IL6R varies with overnight hypoxia ⁴⁶
Oxidative Stress	Endothelin-1 (pg/ml)	Urinary isoprostane 8-epi-prostaglandin F2a (ng/ mmolCr), Oxidized LDL (U/L)	Endothelin-1 implicated in AF ⁵⁷⁻⁵⁹ . Isoprostane ⁶⁰⁻⁶² and oxidized LDL sensitive to SDB ⁷⁶ .

ANALYTIC METHOD BY AIM.

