SA 1. Quantify the extent that SDB and its subtypes are associated with PAF. This aim will be addressed by fitting conditional logistic regression models that condition on the matched pair. We will separately analyze each SDB variable (primary variable: AHI) to obtain an estimate and 95% CI of the odds ratio of PAF for a 1-unit increase in the SDB exposure. Non-linear effects between SDB and the log odds of PAF will be assessed using restricted cubic splines. Knots for the spline will be based on the SDB threshold at which PAF risk increases. Unadjusted and hierarchical adjusted models will be performed using the covariates listed above.

The secondary exposure variables (e.g. hypoxia, OAHI, CAI, AI) will be considered in separate models.

Exploratory Aim 1a. Cardiac structure, autonomic and biochemical variables (Table 2) will explain a proportion of the SDB and PAF relationship. This aim will be addressed by applying Pearl's mediation formula ¹⁰⁸ to the conditional logistical regression model. This approach will allow a causally sound definition of the mediation effect of a given intermediate variable in the relationship between SDB (defined by AHI) and PAF. The approach involves a model for each mediator (e.g. a general linear model for a continuous mediator) and possibly a random effect to account for clustering due to matching and can be thought of as a generalized structural equations model. This approach will allow us to simultaneously assess multiple mediators and will also allow us to consider AHI as a continuous variable. Each model will be fit using likelihood methods and model fit will be checked using appropriate information criteria. After fitting the overall model, we will obtain, for each mediator, an estimate of the indirect effect (e.g. the portion of the overall effect of SDB on PAF mediated through the intermediate variable). A bootstrap resampling technique will be used to obtain a 95% CI for each indirect effect. If the CI does not contain zero, this will indicate statistically significant mediation.

Exploratory Aim 1b. Explore age interactions in the SDB-PAF relationship. Each conditional logistic regression model will include an interaction between age and SDB to investigate if age is a modifier of the effect of SDB on PAF, i.e. whether the odds ratio of PAF for a 1-unit increase in SDB varies by age.

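### Exploratory Aim 1a names no covariates for its mediator models, so for a marker related to PAF within pairs, confounding by BMI or age can be declared significant mediation

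*Combined protocol and SAP*

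**What the plan says.** Sections 9 and 10 carry the same Aim 1a text. Pearl's mediation formula is applied to the SA1 outcome model, which is specified as "fitting conditional logistic regression models that condition on the matched pair". Each mediator gets its own model: "The approach involves a model for each mediator (e.g. a general linear model for a continuous mediator) and possibly a random effect to account for" the clustering that matching creates. That optional random effect is the only provision for the matching. The decision rule is: "A bootstrap resampling technique will be used to obtain a 95% CI for each indirect effect", then "If the CI does not contain zero, this will indicate statistically significant mediation".

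Section 5 describes the matching factors (age ±5 years, gender, race as white versus non-white, BMI ±2 kg/m²) with the words "Matching will be based upon factors which are biologically strong confounders as follows".

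The nearest statement on adjustment belongs to SA1 and comes before Aim 1a: "Unadjusted and hierarchical adjusted models will be performed using the covariates listed above". The list it points to opens "COVARIATES: Age, race, body mass index". It does not include gender. It does include left atrial volume and LVEF, both of which are mediators in Table 2.

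**The concern.** An indirect effect combines two paths, AHI to marker and marker to PAF. Case and control in a pair have similar age, gender, race and BMI, so the pair-conditioned model handles those factors for the second path. The first path comes from a separate model fitted to people from all pairs, where BMI and age vary over their full range.

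A pair random intercept describes correlation within pairs and assumes that the pair effect is unrelated to AHI. That is implausible when pairs are formed on BMI and age. The AHI-to-marker coefficient can then be non-zero with no effect of AHI on the marker. If the marker is also related to PAF within pairs, the interval for the indirect effect can exclude zero, and the study would report a pathway from SDB to PAF that does not exist. Table 2 justifies its primary mediators mainly by known links to AF, so a marker-PAF relation is what the plan expects.

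**Working it through.** **1. The plan's own Aim 1a figure.** Inputs (sections 9 and 10, Power by Aim): PAF probability 0.07 with SDB and 0.01 without, 150 per group, correlation 0.9 between adjusted and unadjusted estimates, proportion mediated 0.5, two-sided 0.05.

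- SE of the difference = √(2 × 0.04 × 0.96 / 150) = 0.0226
- z = 0.5 × 0.06 / (0.0226 × √(2 × 0.1)) = 2.965
- Power = Φ(2.965 − 1.96) = 84.2%

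The stated 84% reproduces as a difference in proportions. On the log-odds scale, which the text's logistic models suggest, the same inputs give 72.2%. Either way it is a power figure and says nothing about false mediation.

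**2. Size of the spurious path.** With standardised variables and no AHI effect on the marker, the AHI-to-marker slope that omits BMI is the product of the two BMI correlations (with AHI and with the marker). The standard error with 300 participants is about 1/√300 = 0.058.

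| BMI correlations | Product | Product / 0.058 | Simulated slope, no covariates | Pair random intercept | BMI included |
|---|---|---|---|---|---|
| 0.3, 0.3 | 0.09 | 1.6 | 0.081 | 0.074 | −0.005 |
| 0.4, 0.4 | 0.16 | 2.8 | 0.149 | 0.133 | −0.001 |
| 0.5, 0.5 | 0.25 | 4.3 | 0.238 | 0.208 | 0.000 |

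The simulated slopes are for a marker unrelated to PAF within pairs. The random intercept removes only about a tenth of the bias.

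**3. False mediation, simulation A.** 150 pairs matched on BMI within 2 kg/m²; true AHI-to-marker effect zero; conditional logistic model with AHI and marker; percentile bootstrap over pairs; 400 studies × 400 bootstraps per scenario. The AHI-PAF odds ratio is 1.5 per SD, the size on which SA1 is powered. Assumptions not in the documents: BMI SD 6, the BMI correlations, BMI-PAF odds ratio 1.3 per SD, PAF uncommon in the source population, matching on BMI only. Entries are the percentage of studies declaring mediation.

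| Marker-PAF OR per SD | Mediator model | 0.3 | 0.4 | 0.5 |
|---|---|---|---|---|
| 1.0 | No covariates or pair random intercept | 1 | 3 | 5 |
| 1.5 | No covariates | 42 | 74 | 84 |
| 1.5 | Pair random intercept | 40 | 69 | 83 |
| 1.5 | With BMI | 9 | 6 | 5 |
| 1.5 | With BMI, controls only | 6 | 5 | 3 |
| 2.0 | No covariates | 64 | 88 | 99 |
| 2.0 | Pair random intercept | 63 | 87 | 98 |
| 2.0 | With BMI | 16 | 12.5 | 12 |
| 2.0 | With BMI, controls only | 6 | 8 | 6 |

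**4. Why BMI alone is not enough.** The sample is half cases. If AHI and marker both raise the odds of PAF, cases are shifted up on both, and pooling them with controls creates an AHI-marker association even at fixed BMI. At correlation 0.3, for an uncommon disease, each shift is about (1 − 0.09) × ln OR: 0.91 × 0.405 = 0.369 for an odds ratio of 1.5 and 0.91 × 0.693 = 0.631 for 2.0.

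- Marker OR 1.5: slope = 0.25 × 0.369² / (0.91 + 0.25 × 0.369²) = 0.034 / 0.944 = 0.036 (simulated 0.033)
- Marker OR 2.0: slope = 0.25 × 0.369 × 0.631 / 0.944 = 0.062 (simulated 0.056)

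This term vanishes if AHI is unrelated to PAF. Pair fixed effects do not remove it: they gave 13, 8.5 and 10% at marker odds ratio 1.5, and 28, 24 and 22% at 2.0.

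**5. Separate runs, same design, pair random intercept.** With no AHI-PAF effect, false mediation was 4–12% at correlations of 0.1–0.2, 24–28% at 0.3/0.3 and 66–68% at 0.4/0.4. With AHI-PAF odds ratio 1.5, it was 38–59% at 0.3/0.3 and 68–85% at 0.4/0.4. At that odds ratio, BMI in the model left 8–9% (marker odds ratio 1.5) to 12–18% (2.0), and fitting in controls with BMI gave 4–5%.

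**The case against.** **The plan is silent; it does not exclude these factors.** A reader might infer that the matching factors are deliberately left out. The documents do not say so. The mediator model is only sketched, and age, race and BMI are on the SA1 covariate list. This stands. But that list is stated for the SA1 conditional logistic models, and nothing extends it to the mediator models. It could not be carried over whole: gender is missing, and left atrial volume and LVEF would be adjusted for while being mediators, with left atrial volume on both sides of its own model. SA3, by contrast, states its own adjusted models.

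**BMI raising both AHI and the marker is not sufficient.** A reader might infer that it is, or that every marker associated with PAF will pass the rule. Neither holds. With a marker unrelated to PAF within pairs, false mediation was 1–5%. With a related one, the rate is well below 100% in most scenarios.

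**The size depends on assumed correlations.** This stands. At 0.1–0.2 with no AHI-PAF effect, the rate is close to nominal. At 0.1/0.1 with AHI-PAF odds ratio 1.5, most of the excess comes from pooling cases and controls: 10.5% without BMI against 8.5% with it at marker odds ratio 1.5, and 22.5% against 18.5% at 2.0. One correlation pair was applied to every marker. Left atrial volume is already indexed to body size (ml/m² in Table 2), which may weaken its relation to BMI.

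**The aim is exploratory.** True, and no primary estimate or sample size depends on it. It still has a significance rule and a power statement, and the abstract lists mediation among the gaps the study addresses.

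**Conclusion.** The concern holds in a conditional form. The mediator models name no covariates, and an optional random effect is the only provision for matching. For a marker related to PAF within pairs, confounding of the AHI-to-marker path by the matching factors can be declared mediation under the stated rule. The simulated false-mediation rate was about 5–10% at assumed BMI correlations of 0.1–0.2 with no AHI-PAF effect, about 25–60% at 0.3/0.3 and about 60–85% at 0.4/0.4, depending on the AHI-PAF and marker-PAF odds ratios. Only BMI was simulated; age may add to it. Adding BMI corrects most of this. When AHI is related to PAF at an odds ratio of 1.5 per SD, it leaves about 8–18% (5–16% in simulation A); fitting in controls with BMI gives about 4–5% (3–8% in simulation A).

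A reader might extend the criticism to the SA1 odds ratio. That does not follow, because SA1 conditions on the pair. Severity is modest.

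**What to change.** In the Aim 1a text of sections 9 and 10, state that:

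- each mediator model includes age and BMI as continuous covariates, and gender and race (white versus non-white), with any pair random effect kept in addition;
- each mediator model accounts for case-control sampling, for example by fitting in controls only or by weighting to the source population;
- the same covariate set is used in the mediation formula and in every bootstrap sample, resampling whole pairs.

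Fitted in controls only, each pair contributes one person and the random effect drops out. Weighting needs a PAF probability, and the plan's power statements use different ones (0.20 at mean AHI for SA1; 0.07 and 0.01 by SDB status for Aim 1a), so the chosen value would have to be justified.

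The cost is four degrees of freedom per mediator model and wider intervals for the AHI-to-mediator path. Using 150 controls instead of all 300 participants widens its standard error by about √(300/150) = 1.41. No new data are needed, since all four factors are recorded for the matching.

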2. OVERVIEW

The *Elucidation of the Influence of Sleep Apnea on Risk of Atrial Fibrillation* study is employs a case control study design to investigate the extent to which there is an independent relationship of SDB and PAF. Cases will be defined as clinically identified patients with PAF and controls as those without AF. In order to rigorously address important biologic confounding influences, the cases and controls will be individually matched based upon age (± 5 years), gender, race (white versus non-white), and obesity ($+/-2$ kg/m 2). Those participants with both PAF and SDB (Apnea Hypopnea Index, AHI ≥ 15) will be asked to return for a follow up exam after 3 months of SDB treatment in the Case Dahms Clinical Research Unit (DCRU) and the Cleveland Clinic CRU for collection of the same measures collected at the baseline exam to observe for any significant changes with the purpose of collecting effect size data to inform future clinical trials.

In addition, ten participants with SDB who are CPAP treatment naive with paroxysmal AF and 10 control participants will be recruited for a sub- study. The 10 participants of the CPAP treatment group undergo MRI scanning before and after 12 weeks of CPAP treatment in a 7T imaging protocol designed to study resting state networks at high spatial resolution. Cognitive testing and questionnaires will be performed before and after treatment. The strength of connectivity between elements of the DMN will be compared before and after treatment. Controls will only be given the cognitive battery and not undergo the MRI brain scan.

The total duration of the study is 4 years. The duration for any individual participant is up to from one to 13 weeks months, including a 3-month treatment period for those with moderate to severe SDB, i.e. AHI ≥ 15 .

Elucidation of the Influence of Sleep Apnea on Risk of Atrial Fibrillation PI- [name] and [name]

Study Time Line

Study Year	1		2			3			4			5				
Calendar Year	2011		2012			2013			2014			2015			2016	
Quarter	3	4	1	2	3	4	1	2	3	4	1	2	3	4	1	2
Hiring, Training, Refining Protocols																
Study Recruitment																
Collection of ECHO Data																
Collection of Continuous ECG Data																
Collection of Biochemical Data																
Data Analysis																

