3. BACKGROUND AND RATIONALE

3. A. 1. Atrial Fibrillation: Burgeoning Epidemic and Need for New Prevention and Treatment Approaches. AF is the most common sustained arrhythmia ³, affecting ~2.2 million individuals in the US ⁴, and potentially up to 16 million Americans by the year 2050 ⁵. AF is an independent predictor of mortality ⁶ and increased stroke, implicated in ~75,000 strokes per year ⁷. Annual costs for AF treatment have been estimated at \$6.7 billion, including \$2.9 billion for hospitalizations ⁸. Therefore, improved AF disease management strategies are needed to reduce hospitalizations and costs ⁹. Furthermore, AF treatments such as ablation and anti-arrhythmic medications are fraught with inconsistent results and pro-arrhythmic side effects ¹⁰. There is a critical need to identify alternative AF treatment and prevention strategies such as those targeting SDB.

3. A. 2. Paroxysmal Atrial Fibrillation: An Ideal Condition to Examine

[figure not shown]
Electrophysiologic Triggers and Diurnal Patterns. PAF is often asymptomatic and occurs early in the continuum of persistent AF development ¹¹. Half of those with PAF have no obvious cause ¹² which may be due to unrecognized triggers such as SDB. The longer PAF persists, the more difficult it is to restore sinus rhythm and prevent recurrence which emphasizes the need to expeditiously identify and address potential contributing factors such as SDB at this stage of disease ¹³. Patients initially presenting with PAF often progress to longer, non-self-terminating bouts ¹³. Importantly, PAF often begins before electrical and extensive structural cardiac remodeling has occurred and provides an ideal substrate for examining acute physiologic triggers such as those that occur in SDB. In individuals with symptomatic PAF, there is a 12:1 ratio of asymptomatic versus symptomatic episodes ¹⁴, therefore continuous ECG monitoring is helpful to provide more detailed, objective data on paroxysms as described in the current proposal. Furthermore, unlike continuous AF, which does not allow reliable detection of autonomic dysregulation via heart rate variability (HRV) indices from ECG data; in PAF, HRV analyses for autonomic function assessment can be derived from the normal sinus rhythm (NSR) period data.

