3. A. 3. Atrial Fibrillation: Unexplained Risk. Given the excess burden of AF and also high prevalence of SDB (~10-15%) ¹⁵, there is a need to better understand AF risk as it pertains to SDB. Hypertension is a risk factor for AF possibly via mechanisms of atrial fibrosis ¹⁶ and left ventricular hypertrophy resulting in atrial dilatation ¹⁷. Obesity is a risk for incident AF based upon Framingham data ¹⁸. A graded relationship between body mass index and progression from PAF to permanent AF in a longitudinal cohort followed over a 21-year period has also been described ¹⁹. However, the role of SDB was not assessed in either study. As increasing SDB has coincided with the obesity epidemic, it is reasonable to suspect that unrecognized SDB would be a contributor to the AF epidemic. Heart failure is also a significant AF predictor ²⁰ and other bidirectional relationships are likely at play. Despite identification of these AF risk factors ²¹, Framingham data as a whole have shown an increased AF prevalence even after adjusting for these known risks ²². Hence, the underlying explanations of increasing AF prevalence have not been completely realized, and investigation of other biologically

plausible risks is critical. The incomplete explanation of AF etiology is “disquieting because, in the absence of identifiable predisposing factors, targeting preventive therapy is difficult”¹³. SDB can be such a factor, and be recognized and managed in clinical practice and in AF pathways for prevention.

3. A. 4. Sleep Disordered Breathing Potentially Accounts for Unexplained Atrial Fibrillation Risk:

Pathophysiology (Figure 1). SDB is a highly prevalent and disabling disorder, afflicting ~15%²³ of adults and as many as 30-50%²⁴ of patients with cardiac disease. SDB exposes the individual to chronic intermittent hypoxemia and wide intrathoracic pressure swings altering autonomic balance, preload and afterload and also enhances inflammatory and oxidative stresses, which operate to bolster a pro-arrhythmogenic milieu. Animal and human experimental studies have identified potential mechanisms by which SDB either through direct or indirect pathways alters the functional and cardiac structural substrate for AF arrhythmogenesis.

1) Direct SDB Effects Potentially Contributing to PAF. (gray boxes and solid arrows in Figure 1)

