6. RECRUITMENT OVERVIEW

The site's study Research Coordinator will oversee recruitment efforts. Patients with PAF who present to Electrophysiology (EP) Clinic at UHCMC and CCF will be approached for recruitment in the study. [name], Director of CCF EP Program and [name] (Co-I), Director of the UHCMC EP Center and 6 other electrophysiologists including [name] (Director of Electrophysiology Research, Co-I) comprise the EP clinical team along with the EP fellowship program/clinic. Approximately 1,680 new patients/year (140/month) with AF are seen in the EP clinics. Of these, ~672 patients/year (~60/month) have PAF. Assuming 50% meet eligibility criteria and 50% of those are interested then ~n=168 patients will be recruited/year (n=14/month). This translates into n=672 potential participants over the 4 year recruitment period which far exceeds the n=150 cases required to meet sample size requirements. As part of clinical care, PAF patients have echocardiograms, may be treated with ablation or anti-arrhythmic medications and often will undergo Holter ECG monitoring. Only those patients with PAF diagnosed within the last 6 months who have not undergone ablation will be approached for enrollment.

A screening form will be designed to identify eligibility criteria. Once a person has been identified as eligible to participate in the study, written informed consent and HIPAA authorization will be obtained. To maintain general descriptive information about the target sample, the screening questionnaires will be entered into a secure research database that does not include any personal identification. All hard copies of this health information will be destroyed about all patients who do not meet study criteria and those who decline participation. All personal health information collected and retained on site prior to obtaining written authorization will be de-linked from identifying personal information. Also, if written authorization is not obtained within 90 days of patients who have agreed to participate in the study, their health information will be destroyed.

Recruitment Sites and Sources

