7. OUTLINE OF STUDY VISITS

Baseline Visit (SA 1 and 2, Table 1). After informed consent, eligible participants will be scheduled to arrive for an overnight visit in the DCRU/CRU within a standardized time interval (< 2 weeks) from informed consent. During the evening, participants will undergo questionnaire administration, blood pressure measurements, application of the MultiSense™ monitoring device, and anthropometry. They will be provided dinner and undergo polysomnography (PSG). In the morning, participants will undergo fasting venipuncture, overnight urine collection, ECHO, 6 minute walk test and blood pressure measurements. For those with PAF (cases), hook-up for continuous ECG monitoring will be performed along with education regarding how to handle the device and bathing instructions, etc. All measurements in the DCRU/CRU will be performed blinded to PAF status. The only unblinded staff will be a dedicated research assistant who will perform the ECG monitoring hook-up. Blinded staff will collect and process data and perform data entry. After the baseline visit, participants with PAF (n=150) will undergo hook-up of the ECG monitor and an activity monitor at the baseline visit to wear for a 7-21 day period. The monitors will be picked up by a courier service. If eligible for the 7T MRI sub-study (cases - AHI \geq 15 and agree to CPAP treatment, controls AHI \geq 15), they will be consented and all questions answered. The individuals who serve as controls who are identified to have sleep apnea (AHI \geq 5) or for those with PAF who have an AHI ranging from 5-15 on the baseline sleep study in the Clinical Research Unit will be notified of these results and the physician will be contacted if the participant provides permission.

Table 1. Timeline of Events for SA 1 and 2	
EVENING	
5PM	DCRU/CRU Arrival/Intake
515PM	Questionnaire Administration
600PM	Anthropometry
630PM	Dinner
9PM	PSG Hook-Up
10PM	Blood Pressure Measurements in Triplicate
1030PM	Lights Out-Overnight PSG
7AM	Lights On/Blood Pressure Measurements in Triplicate
715AM	Fasting Venipuncture
745AM	Overnight Urine Collection
8AM	Echocardiography
830AM	Breakfast
9AM	Continuous ECG monitoring hook-up and education for cases with PAF
930AM	DCRU/CRU Discharge

[figure not shown]
Follow-Up Visit (SA3). Those with SDB (AHI $>$ 15) without evidence of central apnea (central apnea index $>$ 5) or Cheyne Stokes Respirations via baseline visit PSG and who have PAF will undergo the following:

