2) POLYSOMNOGRAPHY (PSG). *Procedure for PSG*: Research PSG will be performed using the Compumedics E-series system (Abbott'sford, AU) which will include 3 cortical encephalograms, bilateral electro-oculograms, a bipolar submental electromyogram, thoracic and abdominal respiratory inductance plethysmography, airflow (by nasal-oral thermocouple and nasal cannula pressure recording), oximetry (using highly sensitive finger pulse oximeter, sampling frequency 25Hz), electrocardiogram (ECG) at 250Hz (used to derive HRV measures of autonomic function); body position (mercury switch sensor), bilateral leg movements. EEGs are recorded at 125Hz. Sensors will be calibrated, and signal quality/impedance checked by a certified technician, using standardized techniques. PSG scoring criteria are documented in the Case Sleep Research Manual of Procedures (**Appendix B**). ***Relevant PSG Variables***: Apneas will be classified as "central" or "obstructive" according to the absence or presence of respiratory effort respectively. Hypopneas will be scored as a 50% amplitude reduction in inductance or flow and associated 3% oxygen desaturation or arousal. Periodic breathing will be defined as airflow or inductance channels increasing and decreasing at least 50% from the maximum, in a cyclic waxing and waning or "sinusoidal" manner for a consecutive period of ≥ 10 min.

Procedure for PSG ECG Signal Extraction: ECG monitoring data from the PSG Baseline and Follow Up Exams will be processed and analyzed by the Case Electrophysiology Core (Director: [name], Nord Professor of Engineering). Data will be exported as European Data Format (EDF) ECG files into customized Matlab programs that

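### Aim 1a mediators are measured after PAF onset in every case, so a marker that SDB affects and PAF itself alters can be declared significant mediation without transmitting any of the SDB effect

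*Combined protocol and SAP*

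**What the plan says.** Aim 1a applies Pearl's mediation formula to the conditional logistic model. The text is the same in sections 9 (Analytic Plan) and 10 (Data Analysis). The plan says: "This approach will allow a causally sound definition of the mediation effect of a given intermediate variable". Each indirect effect gets a bootstrap 95% CI, read as follows: "If the CI does not contain zero, this will indicate statistically significant mediation".

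The order of events is set elsewhere:

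- **Case status (section 2, Overview):** "Cases will be defined as clinically identified patients with PAF and controls as those without AF". Section 5 requires recurrent, self-terminating episodes.
- **Duration of PAF (section 6):** "Only those patients with PAF diagnosed within the last 6 months who have not undergone ablation will be approached for enrollment".
- **Echo, blood and urine markers (section 7):** "In the morning, participants will undergo fasting venipuncture, overnight urine collection, ECHO, 6 minute walk test and blood pressure measurements". This is the baseline visit, after consent.
- **HRV markers (section 8):** derived from the ECG of the baseline sleep study.

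The primary mediators in Table 2 are left atrial (LA) volume, SDNN, hs-CRP and endothelin-1. Aim 1a states no time-order assumption and no sensitivity analysis for reverse causation.

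**The concern.** A mediator has to change before the outcome it helps to cause. Here no case has a marker value from before PAF. If SDB moves a marker and PAF later moves it too, the marker predicts case status at a given AHI. The SDB-to-marker path and the marker-to-PAF coefficient are then both non-zero, and so is their product. The CI rule cannot tell this from SDB acting through the marker.

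This is separate from case-control sampling of the mediator, and it remains if the mediator model is fitted in controls only. The covariate list adds to the doubt, because LA volume and LVEF appear there as confounders and in Table 2 as mediators, so their causal position is not settled.

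At stake is a reported mechanism, and an explained proportion, that may partly or wholly be a consequence of PAF.

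**Working it through.** **1. The plan's own figures.** Sub-Aim 1a states 84% power for a mediated proportion of 0.5 (150 per group, PAF probabilities 0.07 and 0.01, correlation 0.9).

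- Pooled two-proportion test: Z = (0.07 - 0.01) / √(2 × 0.04 × 0.96 / 150) = 2.652.
- Power = Φ(0.5 × 2.652 / √(2 × (1 - 0.9)) - 1.96) = Φ(1.005) = 84%. This reproduces.
- SA1: (1.96 + 0.842)² / (0.2 × 0.8 × (ln 1.5)²) = 298, against the stated 300. This also reproduces.

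Neither figure bears on false declarations of mediation.

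**2. Simulation with zero true mediation.**

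- From the plan: 150 pairs, odds ratio 1.5 per SD of AHI, zero AHI correlation within pairs, CI rule as written.
- Assumed, because the documents give no sizes: c, the SDB-to-marker slope (SD per SD of AHI), and d, the shift in the marker caused by PAF (SD).
- Model: AHI is N(0, 1) in controls and N(ln 1.5, 1) in cases. Marker = c × AHI + √(1 - c²) × noise, plus d in cases only. The marker has no effect on PAF.
- Analysis: conditional logistic regression of PAF on AHI and marker, linear regression of marker on AHI in controls, and a 95% CI for the product of the two coefficients. The product stands in for the mediation formula.

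Percentage of studies declaring significant mediation:

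| Slope c | d = 0 | d = 0.1 | d = 0.25 | d = 0.5 |
|---|---|---|---|---|
| 0.2 | 3.5 | 8 | 32 | 68 |
| 0.3 | about 4 | 13 | 55 | 97 |

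A repeat with a new seed (500 studies per setting, 300 bootstrap resamples of pairs) agrees within about 2 percentage points.

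**3. Weak SDB-marker link.** The rate is about 6% at c = 0, d = 0.5, and 6-10% at c = 0.1, d = 0.25. At c = 0.1, d = 0.5 the repeat gave 22%. There the limit is the chance that the slope itself is significant: z = 0.1 × √150 / √(1 - 0.01) = 1.23, and 1 - Φ(1.96 - 1.23) = 23%.

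**4. Mediator model fitted in all participants.** Aim 1a does not say which participants are used. Pooling cases and controls gives 37-44% at d = 0.2 and 98-99% at d = 0.5 for c = 0.2-0.3, and about 4% at d = 0. With c = 0 and d = 0.5 it gives 16%.

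**5. Spurious proportion.** In this model the marker coefficient is d / (1 - c²), so the false proportion mediated is c × d / ((1 - c²) × ln 1.5), with ln 1.5 = 0.405.

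- c = 0.2, d = 0.5: 0.10 / (0.96 × 0.405) = 26%.
- c = 0.3, d = 0.5: 0.15 / (0.91 × 0.405) = 41%.

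Attenuation of the SDB log odds ratio when the marker is added has the same expected value, so it carries the same bias.

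**6. Direction of a correction.** Take a marker lowered by both SDB and PAF (slope -0.25, shift -0.25). False mediation is 47% as analysed. Subtracting 0.25 SD from the cases doubles the shift and raises it to 86%. Adding 0.25 SD back lowers it to 3.5%.

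**The case against.** The other side has several sound points.

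- **The plan chose early PAF for this reason.** Section 3 argues that "PAF often begins before electrical and extensive structural cardiac remodeling has occurred". Diagnosis within 6 months, exclusion of prior ablation and HRV from sinus-rhythm periods all help, most plausibly for LA volume. They do not exclude a modest shift, and they do nothing specific for the blood and urine markers. The 6 months also run from diagnosis, while section 3 says PAF is often asymptomatic, so onset may be earlier.
- **The plan may seem to call its mediation estimates causally sound.** It does not. That phrase describes the definition of the effect, which is defensible. The overreach is in the CI rule that follows.
- **The protocol may seem to concede that PAF alters these markers.** It does not. The remark "and other bidirectional relationships are likely at play" follows a sentence on heart failure as a predictor of AF and is general. It shows awareness of reverse causation and says nothing about LA volume, SDNN, hs-CRP or endothelin-1.
- **The aim is labelled exploratory.** This lowers the stakes, and the protocol's statements about informing screening and treatment concern the whole study. But Aim 1a still attaches a significance verdict to each mediator, whereas SA3 says expressly that it is not confirmatory.

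**Conclusion.** The concern stands in conditional form. The time order follows from the design, and the rule as written cannot separate mediation from a change caused by PAF. For SDB-marker slopes of 0.2-0.3 and a controls-only mediator model, false declarations rise from about 4% with no PAF-caused shift to 32-55% at 0.25 SD and 68-97% at 0.5 SD.

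A reader might infer that false mediation will be declared. The documents do not support that. They give no size for either path, and at a shift of 0.1 SD, or where SDB hardly affects the marker, the rate is near or only moderately above nominal. The results also rest on normal variables, one mediator at a time and a product-of-coefficients stand-in for the mediation formula. The stated 84% power is not in dispute.

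**What to change.** In sections 9 and 10:

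1. Replace the significance rule. State that a CI excluding zero is an association consistent with mediation only if PAF has not altered the marker.
2. State that the causal wording refers to the definition of the effect under this no-reverse-causation assumption.
3. Add a tipping-point analysis for each marker. Remove an assumed PAF-caused shift of 0, 0.1, ... 0.5 SD from the cases' values, rerun, and report the shift at which the indirect-effect CI first includes zero. Fix the direction beforehand: correct downward for markers PAF would be expected to raise (such as LA volume, hs-CRP, endothelin-1) and upward for those it would lower (such as LA strain or SDNN). Section 3 reports raised SDNN before PAF episodes while Table 2 speaks of reduced SDNN, so SDNN is best run in both directions.
4. State whether the mediator model uses controls only or all participants.
5. If attenuation of the SDB log odds ratio is reported, label it as association.

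The cost is a weaker claim for an exploratory aim and a rerun of existing code. No new data or visits are needed.
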